6.8. Heterogeneity/Poolability

6.8.1. Geography Poolability Analysis

Poolability analysis for the primary endpoint will be performed to evaluate potential difference between studies/regions (US vs. OUS). This analysis will be performed on the AT set for one-month clear population, from the Onyx ONE CLEAR Study and from the Resolute Onyx arm of the Onyx ONE Global RCT Study.

If the resulting test (chi-square test, unless >20% of the expected cell frequencies are less than 5, when Fisher’s exact test will be used) is significant at the 0.15 level, further exploratory analysis will be attempted to identify covariates that may explain differences. Otherwise, the data will be considered to be poolable across studies/regions.

Primary Endpoint by Region

This analysis will be performed in the AT set for one-month clear population. If the resulting test (chi-square test, unless >20% of the expected cell frequencies are less than 5, when Fisher’s exact test will be used) is significant at the 0.15 level, further exploratory analysis will be conducted.

6.8.2. Site Poolability Analysis

If the geographic regions are considered to be poolable, then the site poolability analysis for the primary endpoint will be performed on all sites, regardless of geography; the studies/regions will not be taken into account.

Should, however, the studies/regions not be considered to be poolable, then for the studies/regions, a separate site poolability analysis for the primary endpoint will take place.

Sites should contribute at least 5 subjects to the AT set for one-month clear population. If this is not the case, the site is considered a “small site”; small sites will be excluded from the site poolability analyses.

Revision 4.0

Primary Endpoint by Site

This analysis will be performed in the AT set for one-month clear population. If the resulting test (chi-square test, unless >20% of the expected cell frequencies are less than 5, when Fisher's exact test will be used) is significant at the 0.15 level, further exploratory analysis will be conducted.

6.9. Interim Analysis

No formal interim analysis is planned for this study.

6.10. Additional Analysis

In addition to the analyses described above, other study data such as site report AEs and protocol deviations may be summarized for the AT set and AT one-month-clear population.

There may be additionally 100 subjects enrolled in Japan in this study. Once all enrolled subjects (US and Japan) have had the chance to complete one year follow up, an additional report (including subjects from Onyx ONE Clear Study as well as the Onyx arm of Onyx ONE Global RCT Study) may be prepared as requested by PMDA.

7. Validation Requirements

Statistical programming for the primary endpoint and secondary endpoints, require Level 1 (independent) validation. Other analyses require Level 1 (independent) or Level 2 (Peer review) validation.

8. References

2. Urban P, Abizaid A, et al. LEADERS FREE Biolimus-coated vs. Bare-metal Coronary Stents in High Bleeding Risk Patients. TCT2015.
4. Valgimigli M, et al. J Am Coll Cardiol. 2015;65:805–15.

9. Appendices

Appendix I: Incomplete Date of AE Onset

The following table is guiding on how to input missing dates for AE onset.

Valid Portion	Missing Portion	Imputed Value for missing Portion
Month, Year	Day	Set Day = first day of that month and year, then set the day = later of (New onset date, procedure date).
Year	Day, Month	Set date = later of (January 1 st of that year, procedure date).
None	Day, Month, Year	Date of Procedure

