8.8. Staged Procedures

Treatment of all target lesions with the Resolute Onyx stent within a single PCI is encouraged, if reasonable and safe. However, when staging is required for clinical reasons, the staged procedures should be performed within 30 days from index procedures and similar to index procedure, with a Resolute Onyx stent. A staged procedure is considered a subsequent treatment of a lesion in a vessel not treated at index that is present at the time of the index procedure. Staging should be pre-specified at the time of the index procedure ~~and follow-up should be calculated from the date of index procedure~~. Cardiac enzymes should be obtained before and after the staged procedure, with the same steps as that taken for the index procedure. Lesions and vessels treated with Resolute Onyx stent at the staged procedure are considered target lesions and vessels.

In addition, staged procedures should meet the following requirements:

- Staged procedures must be pre-specified at index procedure AND completed within 30 days of index procedure to qualify as a planned staged procedure. Any additional procedure to the index procedure that does not meet these requirements may be considered as a revascularization and follow-up will be based on the timing of index procedure.
- Resolute Onyx stents should be used at both index and at staged procedures.
- Staged procedures in the target vessel(s) treated at index are NOT allowed.
- Staging should not involve a segment directly adjacent to a segment treated during the index PCI.
- Every urgent coronary reintervention before the planned staged procedure is considered an event.
- Duration of DAPT is one month following the staged procedure.
- For one-month clear analysis, the "clear" definition should be extended to one month beyond the planned staged procedure.
- Follow-up for the one month and two month time points will be calculated from the date of staged procedure; remaining follow ups will be calculated from the index procedure.

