6.1. Analysis Populations

Per the CIP, subjects will be considered enrolled into the trial after the following criteria have been met:

1. The signed and dated informed consent has been obtained
2. The patient and target vessel(s)/lesion(s) have met all of the inclusion and none of the exclusion criteria

Revision 4.0

3. The study stent is introduced into the guide catheter

Intent-to-Treat (ITT): All enrolled subjects. Time zero begins at the date of the index procedure.

As Treated (AT): All ITT subjects who received the Resolute ONYX stent only. Time zero begins at the date of the index procedure.

One-month Clear: All subjects who meet all of the following criteria:

- [REDACTED]
- [REDACTED]
- [REDACTED]

[REDACTED]

[REDACTED]

Event-free is defined as that a subject must not have myocardial infarction (MI) (excluding peri-procedural MIs), repeat coronary revascularization, stroke, stent thrombosis (ARC definite/probable), and death. [REDACTED]

[REDACTED]

As Treated and Intent-to-Treat for one-month clear are:

- As Treated Set for One-month Clear: All AT subjects who are in the one-month clear population. This is the primary cohort for the primary endpoint analysis.
- Intent-to-Treat Set for One-month Clear: All ITT subjects who are in the one-month clear population.

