6.4.2. Primary Endpoint Definition

The primary endpoint is the binary rate of the composite event rate of cardiac death, and myocardial infarction at one-year post-procedure in a one-month clear population. The numerator will be the number of one-month clear subjects who have cardiac death or myocardial infarction, on or before one-year post-procedure (365 days). The denominator will be the number of one-month clear subjects who either have CEC events on or before one year, or have latest date of all follow-up visits, assessments, or events on or after the lower window of one year follow up.

In addition, the KM event rates at 1 month, 2 months, 6 months, 1 year, and 2 years, as well as the KM plot will be provided.

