6.4.3. Data Collection and Analysis Methods

Cardiac death and myocardial infarction events will be adjudicated by the CEC and the data on the CEC adjudication form will be used in the analysis.

The primary endpoint rates in the AT set for one-month clear population will be reported, as well as the two-sided 95% confidence interval. If the upper limit of the two-sided 95% confidence interval is smaller than 9.7%, the primary objective will be considered as a success.

The one-sided binomial exact test will be carried out to assess statistical significance at the 0.025 alpha level.

Revision 4.0

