6.4.5. Missing Data Analysis

Every effort will be undertaken to minimize missing data. One-month clear AT subjects with primary endpoint events, or with CEC events on or before one year, or with any follow-up visits, assessments, or events on or after the lower window of one year follow up will be considered to have complete data for the purposes of this analysis. If outcome data are missing, to assess the potential impact of missing data, a sensitivity analysis will be conducted which will include a complete case (including only subjects whose status is known at one year), a best-case (assume missing Resolute Onyx subjects are event free at one year), a worst-case (assume missing Resolute Onyx subjects have event at one year), and a tipping point analysis if the conclusion is changed in the worst-case analysis.

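### Could the SAP's earliest-date rule for incomplete adverse event dates move endpoint events before the one-month landmark and drop those subjects?

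*SAP*

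**What the plan says.** SAP Appendix I, on incomplete dates of AE onset, has three rows.

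- Day missing: "Set Day = first day of that month and year, then set the day = later of (New onset date, procedure date").
- Day and month missing: "later of (January 1 st of that year, procedure date").
- Whole date missing: the procedure date.

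Each row takes the earliest compatible date, and no visible text in the SAP cites the appendix.

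For cardiac death and MI, SAP 6.4.3 says that "the data on the CEC adjudication form will be used in the analysis". SAP 6.5.1 says the same for secondary endpoints, and Protocol section 5 bases endpoint results on CEC adjudications. Site-reported events appear separately, in SAP 6.10: "other study data such as site report AEs and protocol deviations may be summarized".

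Dates matter for membership of the primary set. Under SAP 6.1, "Event-free is defined as that a subject must not have myocardial infarction (MI) (excluding peri-procedural MIs), repeat coronary revascularization, stroke", stent thrombosis or death, with the one-month time limit given in the protocol glossary. After a planned staged procedure, Protocol 8.8 says the clear "definition should be extended to one month beyond the planned staged procedure". The numerator in SAP 6.4.2 is the one-month clear subjects who "have cardiac death or myocardial infarction, on or before one-year post-procedure (365 days"). The criteria for one-month clear in SAP 6.1, and some text around them, are redacted.

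**The concern.** Appendix I is the only date-completion rule visible in the SAP, and it moves dates in one direction. At the one-month landmark, a rule that only moves dates earlier can only take subjects out of the primary set.

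Take an index procedure on 10 March and an MI in April with the day unknown. The rule gives 1 April, which is day 22. Day 30 is 9 April, so 21 of the 30 possible dates fall after the landmark. The rule would still date the MI to day 22 if a visit on day 30 had recorded no event.

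The sensitivity analyses in SAP 6.4.5 would not recover that subject, because they concern "One-month clear AT subjects with primary endpoint events, or with CEC events on or before one year" and other subjects already classed as clear. Losing a subject with cardiac death or MI lowers the observed rate and so favours meeting the 9.7% goal. Near the boundary, one event decides the result.

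**Working it through.** **Plan's own figure.** Inputs from SAP 5.1 and 6.4.1: n = 1360, goal 9.7%, true rate 6.8%, one-sided 0.025, exact binomial test. The largest passing count is 110: P(X ≤ 110 | 1360, 0.097) = 0.0227 and P(X ≤ 111) = 0.0284. Power is P(X ≤ 110 | 1360, 0.068) = 0.971, which agrees with the stated figure of more than 97%.

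**Share of events that would cross if Appendix I governed endpoint dates.** Assumptions: index dates even over a year, constant event rate, landmark at day 30. Each Appendix I row was applied to every index date and every event day from 31 to 365 (335 days).

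| Missing part | Share moved to day 30 or earlier | Day-equivalents out | Day-equivalents pulled in at day 365 |
|---|---|---|---|
| Day | 4.4% (days 31-60 only) | 14.7 | 14.8 with full follow-up; 5.0 if events are known only to a one-year contact on days 335-395 |
| Day and month | 54% | 181 | 182 or 7, likewise |
| Whole date | 100% | 335 | 0 |

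In the first row, 335 × 0.0439 = 14.7. A landmark delayed by staging changes which days are exposed, but hardly changes that amount.

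**Effect on type I error.** Let f be the share of all cardiac death and MI events dropped at the landmark, with none pulled in at day 365. At a true rate of 9.7% there are 1360 × 0.097 = 132 events. The number dropped is binomial (1360, 0.097f). For each number k dropped, the critical count is re-derived for 1360 − k subjects, and the event rate among those who remain is 0.097(1 − f)/(1 − 0.097f).

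- Day missing for 5% of events: f = 0.05 × 0.0439 = 0.0022, or 0.29 events. Type I error is 0.0241. With full offset at day 365 it is 0.0227.
- Year only for 1%: f = 0.01 × 0.54 = 0.0054, or 0.71 events. Type I error is 0.0264.
- No date for 1%: f = 0.01, or 1.3 events. Type I error is 0.0298.
- Type I error reaches 0.025 at f = 0.0035, or 0.46 events. That needs 0.0035/0.0439 = 7.9% of events lacking the day, or 0.0035/0.54 = 0.64% lacking day and month, or 0.35% with no date.

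**Direction.** Dropping a subject with cardiac death or MI turns 111/1360 (8.16%, fails) into 110/1359 (8.09%, passes). Dropping a subject who had a stroke or repeat revascularization but no cardiac death or MI turns 110/1360 (8.088%) into 110/1359 (8.094%), which works slightly against the goal. An MI with no date would be placed on the procedure date and might be read as peri-procedural. That would not exclude the subject under SAP 6.1, though the event would fall outside the primary window.

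**The case for a change.** The strongest case for acting is that the text is silent on scope, a clarification would cost a sentence or a short paragraph, and an unstated convention could be chosen after the data are seen. Protocol 12.10 bars imputation of outcomes only where nothing else is specified, so it does not settle the point. Contacts after one month may be by telephone or e-mail, source documents in Japan may be limited (Protocol 8.13), and the seven-day reporting limit runs from the site's first knowledge rather than from onset. Small fractions of year-only or undated events would be enough to take the error above 0.025.

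The silence is real, and so is the last point about small fractions. But the events at issue are deaths, MIs, strokes, stent thromboses and revascularizations. For deaths and suspected MI or stent thrombosis, Protocol 8.1.1 has ECGs, angiograms, and admission and discharge records collected for adjudication. Table 9 requires reports within seven days of first knowledge, and Protocol 15.3 provides full monitoring of subject-level data through one year. An adjudicated death or MI with no known month is close to hypothetical. The CEC sets its own minimum data rules, with procedures in a separate charter (Protocol 11.1), and the redacted text in SAP 6.1 is where a timing rule would naturally sit. Neither can be counted as missing.

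A new convention would bring its own difficulty. Placing every unresolved date inside the primary window is conservative for cardiac death and MI. For a stroke or revascularization without either, it keeps a non-event in the denominator and favours the goal.

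**Conclusion.** This is a gap in wording that analysts will fill sensibly. On the plain reading, Appendix I serves site-reported AE summaries and endpoint events carry the date adjudicated by the CEC; then no event moves, and the critical count of 110, the attained level of 0.0227 and the power of 97.1% all stand. If the appendix were misapplied, the only plausible case is a missing day. At an assumed 5% of events, that gives 0.0241 with no offset and 0.0227 with full offset, both under 0.025.

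The documents give no frequency of incomplete dates, so the 5% and 1% inputs are assumptions. The crossing shares also assume even index dates and a constant event rate. The conclusion rests on dates of adjudicated events being known at least to the month, which the reporting, source-record and monitoring provisions support. A note on the scope of Appendix I would do no harm, but it would not change the primary analysis.

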Appendix II: Follow-up Visit Windows

The following table defines the study visit windows.

Follow-up interval	Window
30 days	30 ± 5 days
2 months	60 ± 10 days
6 months	6 calendar months ± 14 days
1 year	1-year anniversary ± 30 days
2 years	2-year anniversary ± 30 days
